9.0 Study Drug Exposure and Compliance

Study drug exposure (days) will be summarized using the sample size, mean, standard deviation, minimum, median and maximum. Study drug exposure will be summarized for overall, two different treatment arms (150 mg or 75 mg) and two diseases (GPP or EP) in the ITT population as follows:

Risankizumab Exposure (in Days):

The Risankizumab Exposure (total duration) will be defined as follows:

The Risankizumab Exposure = Last risankizumab dose date – First risankizumab dose date + 1

10.0 Efficacy Analysis

10.1 General Considerations

The efficacy analysis will be performed for two different treatment arms (150 mg or 75 mg) and two diseases (GPP or EP) in the ITT population. The efficacy analysis will use the data from the study after subjects started to take Risankizumab. The BL values (baseline values) will be used to determine responses and changes in the efficacy variables.

Continuous variables will be summarized by the number of observations, mean, standard deviation, median, minimum, maximum as well as the 95% confidence intervals (CIs) of the mean values. Categorical variables will be summarized by counts and percentages, as well as the 95% CIs of the percentages. No statistical tests will be performed in this study.

Missing data will be imputed using NRI and LOCF methods (see Section 6.0) for the efficacy analyses. And As-Observed Cases (OC) method also will be used for efficacy analyses.

- As-Observed Cases (OC): The as-observed analysis will not impute values for missing evaluations, and thus a subject who does not have an evaluation on a scheduled visit will be excluded from the as-observed analysis for that visit. As-observed analysis will be the secondary approach in the analysis of continuous variables.

10.2 Primary Efficacy Endpoints

The following key efficacy variables will be summarized at all visits in the ITT population for each disease:

For GPP:

- Proportion of subjects achieving a GPP Clinical Response according to JDA total score, defined as at least "Slightly Improved" in the overall improvement rating from baseline, at Week 16.

For EP:

- Proportion of subjects achieving an EP Clinical Response, defined as at least "Minimally Improved" in Clinical Global Impression-Global Improvement (CGI-GI) at Week 16.

10.3 Secondary Efficacy Endpoints

The following additional efficacy variables will be summarized at all visits in the ITT population:

For GPP:

- Proportion of subjects achieving a GPP Clinical Response at Week 52
- Proportion of subjects achieving $\geq 90\%$ reduction from baseline Psoriasis Area Severity Index (PASI) score (PASI 90) at Week 16
- Proportion of subjects achieving PASI 90 at Week 52

For EP

- Proportion of subjects achieving an EP Clinical Response at Week 52
- Proportion of subjects achieving PASI 90 at Week 16
- Proportion of subjects achieving PASI 90 at Week 52

10.4 Other Efficacy Endpoint(s)

The following endpoints will be summarized at each scheduled visit that the respective variable is collected:

For GPP

- Proportion of subjects achieving a GPP Clinical Response, defined at least "Slightly Improved" according to JDA total score in the overall improvement rating from baseline.
- Change from baseline in each of the JDA component scores
- Change and Percent change from baseline in JDA score
- Change and Percent change from baseline in PASI
- Change from baseline in BSA
- Proportion of subjects achieving PASI 50/75/90/100 response

- Proportion of subjects achieving Dermatology Life Quality Index (DLQI) of 0/0 or 1
- Change from baseline in DLQI
- Proportion of subjects achieving at least two grades of improvement in Physician's Global Assessment of Generalized Pustular Psoriasis (PGA-GPP).

For EP

- Proportion of subjects achieving an EP Clinical Response, defined at least "Minimally Improved" in CGI-GI for EP
- Proportion of subjects achieving at least "Much Improved" in CGI-GI for EP
- Percent change from baseline in PASI
- Change from baseline in PASI
- Proportion of subjects achieving PASI 50/75/90/100 response
- Change from baseline in BSA
- Proportion of subjects achieving DLQI of 0/0 or 1
- Change from baseline in DLQI

11.0 Safety Analysis

11.1 General Considerations

Safety analyses will include adverse events, laboratory, local tolerability, ECG, and vital sign measurements.

For the safety analyses, a baseline value (BL) is defined as the last non-missing observation on or prior to the date of the first dose of Risankizumab in this study. Safety summaries will be performed for two different treatment arms (150 mg or 75 mg) total arms, two diseases (GPP or EP) and overall in the safety population. The safety population is same as the ITT population.

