5.3.1.1 Study Procedures

Informed Consent

The subject will sign and date a study specific, Independent Ethics Committee (IEC)/Independent Review Board (IRB) approved, informed consent form before any study specific procedures are performed in order to participate in this study. Details regarding how informed consent will be obtained and documented are provided in [Section 9.3](#).

Inclusion/Exclusion Criteria

Subjects will be evaluated to ensure they meet all inclusion criteria and have none of the exclusion criteria at both the Screening and the Week 0 visit.

Demographics

The subject's demographic data, including date of birth, gender, race, ethnicity, and disease status will be collected at the Screening Visit.

Physical Examination

Complete and targeted physical examinations will be performed at visits as described in [Appendix C](#). Complete physical examination will include general appearance as well as

evaluation of all relevant organ systems. Targeted physical examination will include vital signs assessment and evaluation of organ systems associated with AE(s) symptoms or laboratory abnormalities.

Physical examination findings that are related to subject's medical history will be captured on the appropriate medical history eCRF.

Vital Signs

Vital sign assessment includes temperature, pulse rate, sitting blood pressure, and respiratory rate, after subjects have been seated comfortably for at least 5 minutes.

Measurement of vital signs should precede blood sampling and be assessed pre-dose at all dosing visits. At Visit 2 and Visit 3 additional vital signs will be taken at 5 minutes post-dose and 60 minutes post-dose.

Subjects should be closely monitored for signs and symptoms of hypersensitivity reactions for approximately 2 hours after the first dose administered and 1 hour following all other doses of study drug. Hypersensitivity reactions should be treated according to medical standards. Pre-medications for further injections might be considered and will be agreed on between investigator and AbbVie TA MD.

Body Weight and Waist Circumference

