6.0 Analysis Conventions

Since this is an open-label continuation study, no statistical test will be conducted. Summary statistics will be provided. Data from preceding studies will be integrated with data from this study in the summaries.

Definition of Baseline

For this study, baseline values are defined as the last non-missing values prior to the first dose of study drug in this study. These baseline values will be referred to as "BL" in this document. Unless otherwise specified, this will be the "baseline" for analysis.

Definition of Rx Days (Days Relative to the Date of First Dose of Study Drug)

Rx days are calculated for each time point relative to the date of first dose of this study. They are defined as the number of days between the day of the first dose of risankizumab and the specific time point. Rx days are negative values when the time point of interest is prior to the first risankizumab dose day. Rx days are positive values when the time point of interest is on or after the first risankizumab dose day. The day of the first dose of risankizumab is defined as Rx Day 1, while the day prior to the first risankizumab dose is defined as Rx Day –1 (there is no Rx Day 0).

Definition of Analysis Windows

All time points and corresponding time windows are defined based on Rx Days.

For efficacy analyses, local tolerability, laboratory parameters, and vital sign variables, analysis windows are constructed using the following algorithm:

- Determine the nominal Rx day for each visit (e.g., Week 4 [4 weeks after Baseline visit] equals Rx Day 28).
- In order to include all post baseline data, the first post-baseline interval starts on the first day and the time after the first dose of risankizumab (Rx Day 1).
- Determine the window around a specific nominal Rx day, are presented in the Protocol Appendix C.
- If more than one assessment is included in a time window the assessment closest to the nominal day will be used. If there are two observations equidistant to the nominal day, the one after the nominal day will be used in analyses. If more than one post baseline assessment is included on the same

day, then the worst assessment on that day will be used in analyses, except those specified in Section [11.0](#).

The protocol specified visits and corresponding time windows used in the efficacy analyses, local tolerability, laboratory parameters, and vital sign variables, are presented in the following [Table 1](#) – [Table 32](#).

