Table 1. Visit Windows for Analysis of Clinical Laboratory Tests, Vital Signs, Local Tolerability (WBC, CRP and ALB), and Efficacy Variables (PASI/JDA Score and Responder Rating/PGA-GPP/CGI-GI/BSA)

Window Label	Target Day	Interval
Screening	–	[–42, –1]
Baseline ^a	1	≤ 1 ^b
Week 4	29	[2, 43]
Week 8	57	[44, 71]
Week 12	85	[72, 99]
Week 16	113	[100, 134]
Week 22	155	[135, 176]
Week 28	197	[177, 218]
Week 34	239	[219, 260]
Week 40	281	[261, 302]
Week 46	323	[303, 344]
Week 52	365	[345, 407]
Week 64	449	[408, 491]
Week 76	533	[492, 575]
Week 88	617	[576, 659]
Week 100	701	[660, 743]
Week 112	785	[744, 827]
Week 124	869	[828, 911]
Week 136	953	[912, 995]
Week 148	1037	[996, 1079]
Week 160	1121	[1080, 1142]
Week 172	1163	[1143, 1205]
Week 184	1247	[1206, 1261]
Week 188	1275	[1262, 1282]

Rx Day calculated relative to first dose of risankizumab. For subjects randomized but not dosed, Rx Day calculated relative to Randomization.

- a. There is no baseline for local tolerability measurements and CGI-GI.
- b. If time is collected, restrict to records prior to the first dose of study drug.

Table 2. Visit Windows for Analysis of Clinical Laboratory Tests (excluding WBC, CRP and ALB)

Window Label	Target Day	Interval
Screening	–	[–42, –1]
Baseline ^a	1	≤ 1 ^a
Week 8	57	[2, 85]
Week 16	113	[86, 155]
Week 28	197	[156, 239]
Week 40	281	[240, 323]
Week 52	365	[324, 533]
Week 100	701	[534, 869]
Week 148	1037	[870, 1100]
Week 172	1163	[1101, 1205]
Week 184	1247	[1206, 1261]
Week 188	1275	[1262, 1282]

Rx Day calculated relative to first dose of risankizumab. For subjects randomized but not dosed, Rx Day calculated relative to Randomization.

a. If time is collected, restrict to records prior to the first dose of study drug.

Table 32. Visit Windows for Analysis of Efficacy Variable (DLQI)

Window Label	Target Day	Interval
Baseline	1	$\leq 1^a$
Week 12	85	[2, 99]
Week 16	113	[100, 239]
Week 52	365	[240, 407]
Week 64	449	[408, 491]
Week 76	533	[492, 575]
Week 88	617	[576, 659]
Week 100	701	[660, 743]
Week 112	785	[744, 827]
Week 124	869	[828, 911]
Week 136	953	[912, 995]
Week 148	1037	[996, 1079]
Week 160	1121	[1080, 1142]
Week 172	1163	[1143, 1205]
Week 184	1247	[1206, 1261]
Week 188	1275	[1262, 1282]

Rx Day calculated relative to first dose of risakizumab. For subjects randomized but not dosed, Rx Day calculated relative to Randomization.

a. If time is collected, restrict to records prior to the first dose of study drug.

Definition of Missing Data Imputation

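### SAP 11.1 sets the safety baseline by calendar date, which conflicts with the pre-dose rules in SAP 6.0 and Table 1 for the Visit 2 vital signs

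*SAP*

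**What the plan says.** SAP 11.1 lists vital signs among the safety analyses and takes the safety baseline as the "last non-missing observation on or prior to the date of the first dose of Risankizumab". The limit is a date; no clock time is mentioned.

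SAP 6.0 gives a different general rule: "baseline values are defined as the last non-missing values prior to the first dose of study drug in this study". It adds: "Unless otherwise specified, this will be the 'baseline' for analysis". Both sections label the result BL. SAP Table 1, whose title names vital signs, has a Baseline window running up to and including Rx Day 1, with note b: "If time is collected, restrict to records prior to the first dose of study drug". SAP 11.3 gives laboratory data a baseline of its own, before study drug administration. SAP 11.4, on vital signs and weight, defines none.

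On the readings themselves, Protocol 5.3.1.1 says "Measurement of vital signs should precede blood sampling and be assessed pre-dose at all dosing visits" and "At Visit 2 and Visit 3 additional vital signs will be taken at 5 minutes post-dose and 60 minutes post-dose". Appendix C, note 4, repeats this schedule.

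**The concern.** All three Visit 2 sets of vital signs fall on the date of first dose. A rule that admits anything on that date and then takes the last observation lands on the 60-minute reading, which is a post-treatment value.

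If 11.1 governs, any acute effect of the first injection becomes part of the reference value. Later vital-sign changes would be measured from it, and so would the change criteria in SAP 11.4.1 (20 mmHg systolic, 15 mmHg diastolic, 15 bpm pulse). The bias can run either way: real changes can be hidden, and false flags can be created. Two programmers following different sections of the same SAP could produce different vital-sign tables.

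**Working it through.** The plan gives no figure to reproduce, so the check applies each rule to the same records. For vital signs these are screening, Day 1 pre-dose, Day 1 +5 min and Day 1 +60 min.

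| Rule | Record selected as baseline |
|---|---|
| SAP 11.1 as written | Day 1, +60 min |
| SAP 6.0 definition | Day 1, pre-dose |
| Table 1 note b, time collected | Day 1, pre-dose |
| Table 1 note b, time not collected | Undetermined: all three Day 1 records lie in the window |

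**Which rule prevails.** SAP 6.0 yields where another section specifies otherwise, and 11.1 does so for safety data. Table 1 names vital signs, but its note is conditional. Protocol 5.3.2.1 has the dose time recorded to the minute. Neither document says that clock times are recorded for vital signs, so the condition in note b cannot be confirmed.

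**Other rules that might settle it.** The same-day averaging rule in SAP 11.4.2 covers only post-baseline measurements. SAP 11.2.1 does use clock time for adverse events on the first-dose date. An event starting 60 minutes after the injection would therefore be treatment-emergent, while a blood pressure taken at that moment could count as baseline.

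**Effect on a change.** Let P be the pre-dose reading, S the 60-minute reading and X a later reading. Then

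X - S = (X - P) - (S - P),

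so every later change is shifted by the acute change S - P.

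**Illustration (assumed systolic values).** P = 135, S = 115, X = 112 mmHg.

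- From the pre-dose baseline: 112 - 135 = -23. This meets the decrease criterion of 20, so it is flagged.
- From the 60-minute baseline: 112 - 115 = -3. This is not flagged, and 112 is above the absolute lower limit of 90.
- Check: -23 - (115 - 135) = -23 + 20 = -3.
- The 60-minute reading itself is 115 - 135 = -20 from pre-dose, which also meets the criterion. Used as baseline, it drops out.
- Range: holding P and X, the flag survives only if 112 - S is -20 or lower, that is S of at least 132. A 60-minute fall of more than 135 - 132 = 3 mmHg removes it.
- Reverse case: if the later reading returns to 135, the change is 0 from pre-dose but 135 - 115 = +20 from the 60-minute value, which meets the increase criterion.

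**Where the post-dose readings go.** The text of SAP 6.0 starts the first post-baseline interval on Rx Day 1 after dosing, but the Week 4 window in Table 1 is [2, 43]. Even when correctly kept out of baseline, the Visit 2 post-dose readings fall in no tabulated post-baseline window.

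**The case against.** The strongest reply is that the SAP already has the right rule in the place a programmer would look. Table 1 covers vital signs and restricts baseline to pre-dose records, and SAP 6.0 treats time after the first dose on Day 1 as post-baseline. A reading cannot be both. The protocol also schedules the three sets as distinct time points, so they should be easy to tell apart. Section 11.1 is a general paragraph and does not say that it replaces Table 1.

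Much of this stands. A reader might infer from 11.1 that the 60-minute reading will become the baseline for every later safety change. The documents do not support that:

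- They contain two competing rules, and the one in 6.0 and Table 1 points to the pre-dose value.
- Laboratory baselines are protected by 11.3 and by Protocol 5.1, which makes venipuncture the final procedure before dosing.
- Local tolerability has no baseline (Table 1, note a).
- Efficacy uses the 6.0 baseline (SAP 10.1).
- The absolute flag limits do not involve baseline.
- An acute shift alters a flag only when the two changes fall on opposite sides of the criterion.

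The analyses are also descriptive, and hypersensitivity is monitored clinically for about 2 hours after the first dose, so these tables are not the only safeguard.

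What does not stand is that 6.0 and Table 1 settle the matter. Section 6.0 gives way by its own terms, note b depends on a condition the documents leave open, and 11.1 is the definition written for safety data.

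**Conclusion.** The point holds as a contradiction within the SAP, confined to vital signs. Applied as written, 11.1 selects a post-treatment baseline; 6.0 and, if time is collected, Table 1 note b select the pre-dose value; nothing in the documents decides between them.

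It can affect every dosed subject with Visit 2 post-dose readings (about 16 planned), their vital-sign changes in SAP 11.4.2, and six change criteria in the SAP 11.4.1 table (printed as Table 87): an increase and a decrease for each of systolic pressure, diastolic pressure and pulse. No primary or secondary endpoint is involved. For each subject the distortion equals the acute change from pre-dose to 60 minutes, whose size the documents do not give. The conclusion assumes that the 60-minute set is the last taken that day. The mmHg values are assumed and show only that flag status can change. It should be corrected before database lock.

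**What to change.** - In SAP 11.1, define the safety baseline as the last non-missing observation prior to the first dose of risankizumab, matching 6.0.
- State that the Visit 2 readings at 5 and 60 minutes are never baseline. Where a clock time is missing, let the planned time point decide.
- Summarise those readings as post-baseline Day 1 time points, because the Table 1 Week 4 window starts on Day 2. Exempt them from the same-day averaging in 11.4.2 so that the two time points are not merged.

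The cost is a few sentences in the SAP and a small programming change. Sites need do nothing and no extra data are collected.

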11.2 Analysis of Adverse Events

11.2.1 Treatment-Emergent Adverse Events

Treatment emergent adverse events (TEAEs) are defined as any event with an onset that is after the first dose of risankizumab and with an onset date within 105 days after the last dose of study drug in the analysis period.

- **TEAE of Retreatment:** TEAE are defined as any event with an onset that is after the first dose of retreatment and no more than 105 days after the last dose of study drug.

Events where the onset date is the same as the study drug start date are assumed to be treatment emergent, unless the adverse event start time is prior to the study drug start time. If an incomplete onset date is collected for an adverse event, the event will be assumed to be treatment-emergent unless there is other evidence that confirms that the event is not treatment-emergent (e.g., the event end date is prior to the study drug start date).

The number and percent of subjects experiencing treatment-emergent TEAEs will be tabulated using the Medical Dictionary for Drug Regulatory Activities (MedDRA®) system organ class and preferred term.

Summary tables will be presented as follows:

1. Adverse Event Overview

The number and percentage of subjects experiencing treatment-emergent adverse events will be summarized for the following adverse event categories:

- Any AE
- Any AE that was assessed as related to study drug by the investigator
- Any severe AE
- Any serious AE
- Any serious AE that was assessed as related to study drug by the investigator
- Any AE leading to discontinuation of study drug

- Any AE leading to death
- Any deaths
- Areas of Safety Interest

2. Adverse Events by System Organ Class and Preferred Term

TEAEs will also be summarized and presented using primary Medical Dictionary for Regulatory Activities (MedDRA) system organ classes (SOCs) and preferred terms (PTs). The SOCs will be presented in alphabetical order, and the PTs will be presented in alphabetical order within each SOC.

Subjects reporting more than one adverse event for a given MedDRA preferred term will be counted only once for that term (most severe incident for the severity tables and most related incident for the relationship tables). Subjects reporting more than one type of adverse event within a SOC will be counted only once for that SOC. Subjects reporting more than one type of adverse event will be counted only once in the overall total.

In addition, the number and percentage of adverse events events with causal relationship between the events and the study drug will be summarized using the same conventions described above.

3. Adverse Events by Maximum Severity

The severity grading of AEs follows Rheumatology Common Toxicity Criteria (RCTC).

- Grade 1 – mild
- Grade 2 – moderate
- Grade 3 – severe
- Grade 4 – life threatening

Adverse events will also be summarized by maximum severity. If a subject has an adverse event with unknown severity, then the subject will be counted in the severity category of "unknown," even if the subject has another occurrence of the same event with a severity present. The only exception is if the subject has another

occurrence of the same adverse event with the most extreme severity – ("Life-threatening"). In this case, the subject will be counted under the "Life-threatening" category.

4. Adverse Events by Maximum Relationship

Adverse events will be summarized by maximum relationship to study drug, as assessed by the investigator. Relationship of an AE to study drug is assessed by the investigator and collected in the CRF as 'Yes' or 'No.' If a subject has an adverse event with unknown relationship, the subject will be counted in the relationship category of "unknown," even if the subject has another occurrence of the same event with a relationship of "No." If the subject has another occurrence of the same adverse event with a relationship assessment of "Yes," the subject will be counted under the "yes" category.

A listing of all pretreatment (i.e., events start prior to the first study drug injection) serious adverse events will be provided.

The following tables are planned.

Treatment-emergent adverse events will be summarized as follows:

- Grouped by System Organ Class and Preferred Term
- Grouped by System Organ Class, Preferred Term and Relationship to Study Drug
- Grouped by System Organ Class, Preferred Term and Severity

Treatment-emergent serious adverse events will be summarized as follows:

- Grouped by System Organ Class and Preferred Term
- A by-subject listing will be provided

Pre-treatment serious adverse events will be summarized as follows:

- A by-subject listing will be provided

Treatment-emergent adverse events leading to death or premature discontinuation of study drug will be summarized as follows:

- Grouped by System Organ Class and Preferred Term
- Separate listings by subject for deaths and premature terminations of study drug due to adverse events will be provided.

Treatment-emergent areas of safety interest will be summarized as follows:

- Grouped by System Organ Class and Preferred Term
- A listing by subject will be provided.

Areas of Safety Interest:

Areas of Safety Interest groupings are listed in [Table 43](#). These events are of interest due to a higher rate in the moderate to severe psoriasis population, or of interest for all Ig products or products in general (DILI).

The final list will be based on the most updated final version of risankizumab Product Safety Statistical Analysis Plan, which is consistent to the most updated risankizumab Risk Management Plan.

Grouped Terms

Grouped terms will be summarized by grouped term or SMQ, including sub-SMQs and preferred term for any adverse event, adverse events leading to discontinuation, serious adverse events, moderate or severe adverse events and related adverse events.

Table 43. Areas of Safety Interest

ASI Grouping	Categories (ASI)	Search Criteria	Terms to Display	Include in AE Overview (Y/N)
Adjudicated CV Events	Major adverse cardiovascular events (MACE)	Adjudicated events	
Display underlined terms defined by the following adjudicated terms:
 
 • CV Death which includes CETERM values: Fatal CV, Fatal PE, Fatal Non-Cardiac/Non-Neuro Arterial Thrombosis/Thromboembolism, Undetermined Death, Not assessable death (cardiac/neuro/thrombotic), Fatal Stroke • Myocardial infarction • Stroke 	Y
	Extended MACE	Adjudicated events	
Display underlined terms from MACE and underlined terms below:
 
 • Hospitalization for Unstable Angina • Coronary Revascularization Procedures 	N
	Other CV events	Adjudicated events	
Display underlined terms defined by the following adjudicated terms:
 
 • Thrombotic events which includes CETERM values: Deep Vein Thrombosis, TIA, Pulmonary Embolism, Non-fatal Non-Cardiac/Non-Neurological Arterial Thrombosis/ Thromboembolism, Other Venous Thrombosis, specified (non-fatal) • Cardiac arrhythmia which includes CETERM of: Clinically Significant Arrhythmia • Congestive heart failure which includes CETERM of Heart Failure • Hypertensive emergency 	N

Table 43. Areas of Safety Interest (Continued)

ASI Grouping	Categories (ASI)	Search Criteria	Terms to Display	Include in AE Overview (Y/N)
Possible Drug induced liver injury (DILI)	Possible Drug induced liver injury (DILI)	Broad – Hepatic failure, fibrosis and cirrhosis and other liver damage-related conditions (SMQ 20000013) Broad – Hepatitis, non-infectious (SMQ 20000010) Broad – Cholestasis and jaundice of hepatic origin (SMQ 20000009) Broad – Liver related investigations, signs and symptoms (SMQ 20000008) Narrow – Liver-related coagulation and bleeding disturbances (SMQ 20000015)	PTs	Y

Adverse Event per 100 Patient-Years of Exposure

Adverse events occurring during the entire study will be presented by event rate per 100 patient-year. These will be presented for any TEAEs, serious adverse events, Areas of Special Interest.

AEs per 100 patient-years of exposure is defined as the number of AEs divided by the total exposure in 100 patient-years. Note that one event per preferred term per day per

subject will be counted in the calculation of the number of AEs (i.e., a preferred term will not be counted twice on the same day for the same subject). See the calculation method below.

$$100 \times \frac{\text{Number of TEAEs}}{\text{Total Patient Years}}$$

where total patient years is defined as the sum of the study drug exposure (defined as date of last dose – date of first dose + 105 days (5 half-lives)) of all subjects normalized by 365.25, and rounded to one decimal place.

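### In the maximum-severity adverse event table, a subject with a known Grade 3 and an ungraded occurrence of the same event is counted as unknown, not severe

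*SAP*

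**What the plan says.** SAP 11.2.1 item 3 grades adverse events on four levels, of which the top two are "Grade 3 – severe" and "Grade 4 – life threatening". Where a grade is missing, one ungraded occurrence is enough to move the subject to *unknown*, and this applies "even if the subject has another occurrence of the same event with a severity present". The one exception is a subject who also has a life-threatening occurrence of the same event; that subject is counted as life-threatening.

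Item 2 of the same section gives the general convention. A subject is counted once per preferred term, using the "most severe incident for the severity tables and most related incident for the relationship tables".

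Item 1, the adverse event overview, has its own row for subjects with any severe event. No rule for unknown severity is given there.

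Item 4, on relationship to study drug, also has an *unknown* category. There, a known Yes on another occurrence takes precedence, and the subject is tabulated as related.

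**The concern.** A maximum-severity table is read mainly for its severe and life-threatening rows. Under item 3 a recorded Grade 3 event does not put the subject in the severe row if another occurrence of that event lacks a grade. The true maximum is then uncertain, but only between Grade 3 and Grade 4; it cannot be lower. The *unknown* label throws that information away. For this table, compared with keeping a known Grade 3, the rule can only lower the severe row. Safety is one of the primary objectives (SAP 4.1), and with so few subjects each cell is read individually.

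Several records of one event at different grades are to be expected: protocol 6.1.1.1 has a worsening in severity reported as a new event, and treatment runs for 172 weeks.

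**Working it through.** The plan states no figure to reproduce, so the check applies the counting rule to every case.

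**Inputs.** Grades 1 to 4 and the *unknown* rule with its Grade 4 exception: SAP 11.2.1 item 3. At least 8 subjects per substudy, at least 16 in total: SAP 4.3. Allocation 1:1 within each substudy: SAP 5.1. Assumptions: *same event* means same preferred term, and arms split evenly at the minimum size.

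**Step 1, the cases.** For one event, a subject's occurrences form a non-empty subset of {1, 2, 3, 4, U}, where U is ungraded. There are 2^5 − 1 = 31 subsets.

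**Step 2, the result under three rules.**

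| Occurrences | Number of sets | SAP item 3 | Highest known grade | Grade 3 also overrides |
|---|---|---|---|---|
| No U | 15 | highest grade | same | same |
| U only | 1 | unknown | unknown | unknown |
| U with a 4 | 8 | life-threatening | life-threatening | life-threatening |
| {3,U}, {1,3,U}, {2,3,U}, {1,2,3,U} | 4 | unknown | severe | severe |
| {2,U}, {1,2,U} | 2 | unknown | moderate | unknown |
| {1,U} | 1 | unknown | mild | unknown |

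The sets add up: 15 + 1 + 8 + 4 + 2 + 1 = 31. Item 3 departs from the highest known grade in 4 + 2 + 1 = 7 sets. In 4 of these the highest known grade is Grade 3, and all 4 are tabulated as *unknown*. These are counts of possible patterns, not probabilities.

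**Step 3, the scale of one subject.**
- Dose arm within a substudy: 8/2 = 4 subjects, so 1/4 = 25%.
- Substudy: 1/8 = 12.5%.
- Overall: 1/16 = 6.25%.

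**Step 4, agreement between outputs.** Read as written, the overview's severe row includes a subject with a recorded Grade 3 event, because nothing there diverts the subject to *unknown*. The maximum-severity table does divert the subject. The two outputs can then give different severe counts from the same data, and the SAP does not say which rule governs the overview.

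**The case against.** The best defence is that only the top category settles a maximum when one value is missing. With Grade 3 plus ungraded, the truth may be Grade 3 or Grade 4, so *unknown* is a literally accurate label. Item 3 can also be read as a specific missing-data rule that refines the general convention in item 2. Both points have force, so the two items fit poorly together but do not flatly contradict each other. What remains is that the rule gives up a known lower bound.

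A reader might infer that the relationship rule exposes an inconsistency, since a known Yes overrides *unknown* there. It does not: Yes is the top of a Yes/No scale, so both rules let only the top category override.

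A reader might also infer that severe events disappear from the report. The documents do not support that. The subject remains in the same table under *unknown*. The overview row is not stated to follow the rule, and grouped terms are also summarised for moderate or severe events. Serious events, deaths, discontinuations and areas of safety interest have by-subject listings. SAP 11.2.1 states no listing for a non-serious Grade 3 event outside those groups; the output list in SAP section 17 was not available for this check and may contain one.

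Missing grades should be rare. Protocol 6.1 requires severity to be recorded for each event, protocol 10.2 has case report forms reviewed for completeness, and protocol 11.0 plans logic and manual checks. They are more plausible at the interim analyses. SAP 4.4 uses all safety data received by cut-off, while the cleaning condition for the first interim covers data up to Week 28 and none is stated for the Week 52 interim.

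Finally, using the highest known grade throughout would show {1,U}, {2,U} and {1,2,U} as mild or moderate although the ungraded occurrence could be worse. That objection stands, and it argues for a narrower change.

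**Conclusion.** The point holds for one table. Item 3 omits from the severe row a subject whose maximum is known to be at least severe, and that table may disagree with the overview. The effect requires the same subject to have both a Grade 3 and an ungraded occurrence of the same event. The documents give no rate of missing grades, so it is possible, not expected. A reader might take 25% as the likely distortion, but it is only one subject in an assumed arm of four; the share is smaller in the substudy and overall summaries, and no statistical test depends on the cell. This is a low-priority improvement, worth making because it costs almost nothing.

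**What to change.** Amend the exception in SAP 11.2.1 item 3 so that a known Grade 3 as well as a known Grade 4 overrides *unknown*, with the subject counted at the highest known grade. Leave Grade 1 or 2 plus ungraded in *unknown*, so that a possibly higher grade is not shown as mild or moderate. Footnote the number of subjects with any ungraded occurrence. In item 1, state that the severe row of the overview counts any subject with a recorded event of Grade 3 or higher.

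The change moves the 4 patterns identified above from *unknown* to severe and leaves the other 27 as they are. It needs a few sentences in the SAP and no new data. There are two downsides: a small departure from the sponsor's convention, and the possibility that a subject shown as severe was in truth Grade 4, which the footnote discloses.
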